#### 4.3 Recruitment

20 participants will be recruited by the study investigators from their epilepsy clinics at The Hospital for Sick Children. During a routine visit, patients/parents/caregivers that meet criteria for the study will be asked if they would like to participate in the study. If they are interested in participation then eligibility will be assessed using our inclusion

and exclusion criteria. Patients who have previously been treated with a Cannabinoid product, must have stopped taking it at least 60 days before enrolment, and they will be asked for a urine test (5-10 ml) to assess for the presence of Tetrahydrocannabinol (THC) in urine. A negative urine test for THC will confirm their eligibility to the study. There is published clinical trial evidence for Epidiolex (a cannabinoid product) as an anti-epileptic agent, and Health Canada approved Cannabinoid product use over a year ago, therefore many families have tried this product, and it is not feasible to expect CBD naïve participants, nor is it necessary. A washout period is sufficient. A wash out period of 60 days allows for all of the administered cannabinoid products to be eliminated from the participant's body. All genders and ethnicities will be included between ages of one and eighteen years. The physician will explain the study during the routine visit. If the patient/parent/caregiver agrees, they will be given the informed consent documents to read and sign. Only the Principal Investigator, Sub-Investigators, and other research personnel listed on the study will have access to participant's research files.

#### 4.4 Withdrawal from the study

##### 4.4.1 When and How to Withdraw

Study participant may withdraw or be withdrawn from the study at any time if the participant, parent/caregiver, or Investigators feel it is not in the participant's best interest to continue. Study participation may be discontinued in the following circumstances:

1. Parent/ legal guardian withdrawal of consent
2. Participant non-compliance with study procedures
3. Serious adverse events, including significant toxicity, impaired liver or renal function, or impaired hematopoiesis
4. Exacerbation of seizures not attributable to another factor

#### 5. Interaction with participant concomitant AED regimen causing unacceptable toxicity

Once the study withdrawal is decided, the termination of treatment is determined based on reason for withdrawal. For example if participant has a severe allergic reaction with rapidly progressive rash the treatment would be abruptly stopped, whereas if the participant experiences excessive somnolence, the treatment may be withdrawn in a gradual way. This determination will be made on an individual basis by study team in consultation with participant and participant's parent/caregiver.

#### 4.4.2 Data Collection

For all participants who withdraw from the study we will invite them to attend a clinic evaluation within 4 weeks of withdrawal +/- 2 weeks. During this visit we will document: their dose reached, reasons for withdrawal, adverse events, seizure diary and PESQ will be assessed, patients will have a physical and neurological examination and AED trough levels and routine bloodwork (CBC, LFT, Renal profile).

#### 4.4.3 Replacement

Participants will not be replaced following withdrawal in the study

#### 4.4.4 Follow-up

Every participant will be followed closely throughout the study and if a withdrawal occurs contact will be made with participant and they will be invited to attend a final clinic visit as described above. If the participant cannot be contacted after 4 phone calls, a letter requesting the participant's parent / legal guardian to contact the study investigator team will be sent to participant household.

## **5. Study Treatment**

### 5.1 Study Drug

Tilray TIL-TC150 is formulated with THC and CBD in grape seed oil at strengths of 2 mg/ml and 100 mg/ml, respectively. The product is formulated with standard pharmaceutical excipients. The active ingredients in TIL-TC150 Oil are THC and CBD, present in a 1:50 ratio. These active ingredients are derived from *Cannabis sativa* L. strains produced by Tilray, a federally-licensed producer and distributor of medical cannabis under Health Canada's Marijuana for Medical Purposes Regulations. The details of extraction and formulation are laid out in the Tilray investigators brochure (part of submission)

### 5.2 Treatment Regimen

Each participant will start the treatment with a dose of 2mg/kg/day CBD given in two equal doses each day. The first dose will be given during the Baseline (Week 0) visit. Following this dose the participant will be observed by study personnel for a period of 2 hours. The participant's parent/legal guardian will increase the participant's dose by 2mg/kg/day CBD every 7 days as tolerated, to a maximal dose of 16mg/kg/day CBD. Once optimal dose is determined for each participant they may continue the treatment for the duration of study follow-up and thereafter it will be continued if wished by participants.

### 5.3 Concomitant treatments

Participants will be taking concomitant AED, perhaps 1-4 AEDs. In addition they may have a VNS device inserted or be on the ketogenic diet. We require that their current regime is stable prior to initiation – 4 weeks for AED and 3 months for VNS and ketogenic diet. All concomitant anti-epileptic treatments are to be continued during the intervention period. Participants who are currently taking AEDs where trough levels can

routinely be assessed, will have levels assessed at interval throughout the study intervention period (as per the detailed schedule) to ensure safety.

### 5.3 Compliance Monitoring

Study drug compliance will be assessed by clinic evaluations and the follow-up phone calls and emails as outlined in earlier section. In addition we will ask dispensing hospital research pharmacist to measure the mls remaining in their bottle of Cannabinoid when they return to collect a next prescription. Any participant who is not compliant with the study treatment regime will be withdrawn from the study.

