## 1.2 Investigational Product

The physiochemical characteristics of THC and CBD are detailed in Table 1.

| Table 1: Drug Substance Common Name | delta-9-tetrahydrocannabinol (THC) and cannabidiol (CBD)  |
|--|---|
| Chemical Name                       | THC: IUPAC ID: (-)-trans- $\Delta^9$ -tetrahydrocannabinol; IUPAC ID: (-)-(6aR,10aR)-6,6,9-trimethyl-3-pentyl-6a,7,8,10a-tetrahydro-6H-benzo[c]chromen-1-ol.
CBD: IUPAC ID: 2-[(1R,6R)-6-isopropenyl-3-methylcyclohex-2-en-1-yl]-5-pentylbenzene-1,3-diol. |
| Appearance                          | THC: Light yellow resinous oil; CBD: Light yellow resinous oil  |
| Molecular Formula                   | THC: C 21 H 30 O 2 ; CBD: C 21 H 30 O 2   |
| Molecular Mass                      | THC: 314.47; CBD: 314.47  |
| Solubility                          | THC: Soluble in methanol, ethanol, acetone, chloroform, and dichloromethane. Insoluble in water.
CBD: Soluble in methanol, ethanol, acetone, chloroform, light petroleum, and dichloromethane. Insoluble in water.   |

Tilray TIL-TC150 is formulated with THC and CBD in grape seed oil at strengths of 2 mg/ml and 100 mg/ml, respectively. The product is formulated with standard pharmaceutical excipients.

TIL-TC150 Oil is packaged in 25 ml Type III amber glass stopper bottles with a polypropylene cap and a fill of 20.0 ml. The oil drug product is stored at room temperature with a 6 months expiration.

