## **10. Quality Control Procedures**

The study pharmacist will oversee the dispensing of the study treatment to the participant parent/caregiver and keep documentation of this. Study investigators will document all clinical details throughout the study in CRFs and in source documentation. Principal investigator will make time to review the documentation, source documentation and ensure that it is readily available for any reviewing agency at any time. In addition study investigator team will ensure confidentiality is maintained throughout the data process. This will be overseen by study Principal Investigator as detailed below.

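### The volume check in section 5.3 reads the residue of one bottle, which cannot reliably quantify under-dosing once several 20 mL bottles are dispensed, and no analysis uses the result

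*Combined protocol and SAP*

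**What the plan says.** Section 5.3 (Compliance Monitoring) relies first on clinic evaluations and on follow-up phone calls and emails. As an added step, the dispensing research pharmacist is to "measure the mls remaining in their bottle of Cannabinoid when they return to collect a next prescription". It closes with: "Any participant who is not compliant with the study treatment regime will be withdrawn from the study".

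The product facts are in section 1.2. THC and CBD are formulated "at strengths of 2 mg/ml and 100 mg/ml, respectively", and each bottle has "a fill of 20.0 ml". Section 5.2 sets the regimen: "Each participant will start the treatment with a dose of 2mg/kg/day CBD given in two equal doses each day". Parents then raise the dose by 2 mg/kg/day every 7 days as tolerated, "to a maximal dose of 16mg/kg/day CBD".

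Section 10 adds: "The study pharmacist will oversee the dispensing of the study treatment to the participant parent/caregiver and keep documentation of this". Between visits, caregivers are asked what dose the child is on (section 5.7). The primary endpoint is the maximal safely tolerated dose (section 3.4), and the Study Summary plans descriptive statistics on adverse events by dosage.

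The plan does not state how many bottles are dispensed at a time, how often families refill, whether all bottles come back, what volume is expected, or what counts as non-compliance.

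**The concern.** The dose is raised and given at home by parents, and the primary endpoint is a tolerated dose. If a family gives less than prescribed, perhaps because of side effects, and does not say so, the child is recorded as tolerating a dose that was not taken. That biases the tolerated dose upward and the adverse event frequency at that dose downward.

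The bloodwork in sections 5.6 and 5.7 covers blood count, liver and renal function and concomitant AED levels. No CBD or THC level on treatment is described. The volume check is thus the only objective evidence of intake in the plan, so it matters whether it can measure what it is meant to measure.

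**Working it through.** The plan gives no expected volume or bottle count to reproduce, so the check starts from the product and dose figures.

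**Inputs from the documents:** fill 20.0 mL and CBD 100 mg/mL (section 1.2); start 2 mg/kg/day, steps of 2 mg/kg/day every 7 days, maximum 16 mg/kg/day (section 5.2); clinic visits at weeks 0, 2, 4, 8, 12, 16, 28, 40, 52 and 64 (sections 5.6 to 5.8).

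**Assumptions:** body weight W of 10 to 60 kg (the plan gives only an age range, 12 months to 18 years); refills at clinic visits; the smallest sufficient number of whole bottles dispensed.

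**Step 1, how long a bottle lasts.** One bottle holds 20 × 100 = 2000 mg CBD. Days per bottle = 2000 / (dose × W). Volume at 16 mg/kg/day = 16 × W / 100 = 0.16 × W mL/day.

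| W | Days per bottle at 2 mg/kg/day | Days per bottle at 16 mg/kg/day | mL (bottles) per 28 days at 16 | mL (bottles) per 84 days at 16 |
|---|---|---|---|---|
| 10 kg | 100 | 12.5 | 44.8 (2.2) | 134.4 (6.7) |
| 30 kg | 33.3 | 4.2 | 134.4 (6.7) | 403.2 (20.2) |
| 60 kg | 16.7 | 2.1 | 268.8 (13.4) | 806.4 (40.3) |

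**Step 2, what one open bottle shows.** Let E be the expected volume, N the bottles dispensed and f the fraction missed. Total left = 20N − (1 − f)E. The open bottle shows only the part of this that remains after removing whole unopened bottles. At 30 kg for 28 days at 16 mg/kg/day, E = 134.4 mL and N = 7 (140 mL):

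| Missed | Volume used | Total left | Unopened bottles | Open bottle only |
|---|---|---|---|---|
| 0% | 134.4 | 5.6 | 0 | 5.6 mL |
| 10% | 121.0 | 19.0 | 0 | 19.0 mL |
| 20% | 107.5 | 32.5 | 1 | 12.5 mL |
| 30% | 94.1 | 45.9 | 2 | 5.9 mL |

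The total rises steadily with the missed fraction. The open-bottle reading does not: 30% missed looks like full compliance, and 10% missed looks worse than either 20% or 30%.

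**Step 3, why.** The open-bottle reading repeats each time another 20 mL goes unused, that is, every 20/E of the dose. Over 28 days at 16 mg/kg/day this is 20/44.8 = 45% at 10 kg, 20/134.4 = 15% at 30 kg and 20/268.8 = 7% at 60 kg. Over 84 days it is 15%, 5% and 2.5%.

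**Step 4, early titration.** Weeks 0 to 2 need 7 × (2 + 4) × W / 100 = 0.42 × W mL: 4.2 mL at 10 kg, 12.6 mL at 30 kg and 25.2 mL at 60 kg. At 30 kg one bottle suffices. It would hold 20 − 12.6 = 7.4 mL with full compliance and 20 − 0.7 × 12.6 = 11.2 mL with 30% missed. Here the single-bottle reading works.

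**Step 5, size of a miscredited dose.** In the Step 2 example, 30% missed at a prescribed 16 mg/kg/day means 0.7 × 16 = 11.2 mg/kg/day taken. The gap of 4.8 mg/kg/day is 2.4 titration steps. Each child is 1/20 = 5% of the planned cohort.

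**The case against.** A reader might infer four stronger things that the documents do not support.

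- *That compliance is judged from the bottle alone.* It is not. Contacts come first in section 5.3 and are frequent up to week 18: clinic at weeks 0, 2, 4, 8, 12 and 16, phone or email at weeks 1, 3, 5, 6, 7, 10, 14 and 18.
- *That the check can never show under-dosing.* The singular noun may be loose wording. A dispensing record exists (section 10), the check is tied to collecting a prescription rather than to a visit, and one bottle is informative at early doses. Shorter refill intervals or lower tolerated doses would also make the reading more useful. Over-use would probably show as early refills in that record.
- *That the achieved dose is derived from the residue.* No section says so. Dose comes from caregiver report and study-team determination; the volume could only corroborate it.
- *That the residue triggers withdrawal.* Section 5.3 attaches withdrawal to non-compliance with the treatment regime, which it does not define, and does not name the residue as the trigger.

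All four replies stand and limit the point. They do not remove it. If practice already reconciles every bottle, the protocol does not say so. Analysing all participants whatever dose they reached (section 8.1) keeps them in the denominator, but does not correct a dose that was recorded and not taken. Caregiver report is itself the thing that needs corroborating, and no phone or email contacts are listed after week 18, when visits move to 12-week intervals.

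**Conclusion.** The point holds in a limited form. As written, the only objective check on intake reads one bottle. At the higher doses, with refills at 4-week or 12-week visits, that reading cannot reliably quantify under-dosing or rank children by compliance: 5.6 mL against 5.9 mL for 0% against 30% missed in the 30 kg example. It also feeds no analysis, although the endpoint is a tolerated home dose.

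The size depends on assumed weights of 10 to 60 kg, on refills at visits and on a constant 16 mg/kg/day. The documents show that the bias is possible. They do not show that it will occur, or in which children.

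A separate wording conflict needs attention. Section 5.3 makes withdrawal for non-compliance with treatment mandatory, while section 4.4.1 lists non-compliance with study procedures among reasons for which participation may be ended. The two must be reconciled.

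**What to change.** Amend section 5.3 so that families return all bottles, opened and unopened, whenever they collect a prescription. For each child and interval, record:

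- taken = total mL dispensed (including any carried over) − total mL returned;
- expected = sum over days of prescribed mg/kg/day × weight / 100, using the dated prescribed dose steps;
- taken/expected as a percentage, and achieved mg/kg/day = 100 × taken / (weight × days). In the 30% example this gives 100 × 94.08 / (30 × 28) = 11.2.

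Record unreturned bottles as missing, and do not count their contents as taken. Report achieved beside prescribed dose in the tolerability and adverse event tables, and keep every participant in the analysis.

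Dispensing is already documented, and section 5.6 has children weighed at the intervention visits. Section 5.7 does not name weighing at weeks 28 to 64, so the amendment should say which weight applies there.

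The cost is that families bring back all bottles and the pharmacist totals the volumes. Because the check already happens at prescription collection, no added visit is apparent. The method measures oil that has left the bottles, so spilled or discarded oil would still count as taken.

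Reconcile the withdrawal wording of sections 5.3 and 4.4.1 in the same amendment.

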### 5.4 Enrollment

All participants meeting inclusion and exclusion criteria will be invited to enroll during a clinic visit at The Hospital for Sick Children with the study investigator team. The participant's legal guardian/parent will be given a consent form to read and the study will be explained to them by a physician member of the study team. Given the level of intellectual impairment associated with Dravet syndrome, we do not anticipate a participant will have capacity to consent or assent to participation in the study and thus a single parent/legal guardian consent form has been created.

### 5.5 Pre-Intervention Period (4 weeks)

Once enrolled, the pre-intervention period begins. Participants will be seen and baseline physical and neurological examination performed. Medical information regarding seizures, medications, birth and development will also be collected. Participant parent / legal guardian will be instructed to keep a daily seizure diary for the next four weeks which will be used as a measure of baseline seizure frequency. Seizure diary will be kept by participant's parent/ legal guardian for the duration of the study follow-up period also. Seizure frequency for each seizure type will be recorded at baseline. Seizure types will be classified prior to study entry.

- A. Diary: Seizure frequency and type will be monitored and recorded in a participant's daily diary. Participant's parent/caregiver will report the seizure frequency, type, number of episodes of Status Epilepticus, use of rescue medication and attendance to ER/ hospitalizations.
- B. Prolonged EEG study: During the pre-intervention period each participant will have a 24 hour ambulatory EEG recording performed to enable objective measurement of a 24 hour sample of electrographic activity – ictal and interictal, which will be reported by a certified experienced Clinical Neurophysiologist who is not part of the investigator team.
- C. Vineland Adaptive Behaviour Scale, Second Edition: this is a standardized parent interview that will take 20-60 minutes to complete either in person at the clinic or by telephone prior to starting the TIL-TC150. The interview will also be completed again at the primary evaluation period (week 16-20) and again during the longitudinal follow-up (52-64 weeks). This will be done by a clinical research assistant, under supervision of a clinical neuropsychologist (Dr. [name], CPsych). Parents will be provided with a research report detailing the assessment findings at study completion.

#### 5.6 Intervention Period – and Primary Evaluation (20 weeks)

Week 0: (Baseline): A neurological and physical exam (including measurement of vital signs) will be performed and the participant will be weighed. The parent / legal guardian will complete the QOLCE. During this visit their seizure diary will be evaluated and bloodwork will be performed for baseline measures (Complete blood count, LFT (AST ALT, gamma GT, bilirubin), renal profile (electrolytes, creatinine and urea), and AED trough levels). The participant's parent/legal guardian will be instructed on dosing and twice daily administration of TIL-TC150. Each participant will start TIL-TC150 at an initial dose of 2mg/kg/day CBD in 2 equally divided doses, this will be added to their current anti-epileptic drug therapy regimen. They will be advised to increase the dose of the study treatment after 7 days by 2mg/kg/day CBD. The study pharmacist will be present

at the first clinic visit to review dosing schedule, administration and pharmacy dispensing procedures. In addition study pharmacist will be available during the study period to provide education and support to families. The first dose will be administered in clinic and the participant will be observed for a period of 2 hours by study personnel to evaluate for any adverse events.

Week 2: Participant to return to The Hospital for Sick Children. Study treatment increased as tolerated by 2mg/kg/day CBD, neurological and physical exam will be performed and the participant will be weighed, and seizure diary evaluated. Medical history including concomitant medications will be reviewed. The Pediatric Epilepsy Side Effect Questionnaire (PESQ) will be completed by participant's parent/legal guardian to assess for any adverse events and tolerability.

Week 4: Participant to return to The Hospital for Sick Children. Study treatment increased as tolerated by 2mg/kg/day CBD, neurological and physical examination will be performed, weight recorded, seizure diary evaluated. Bloodwork performed (CBC, LFT, Renal profile, AED trough levels). Medical history including concomitant medications will be reviewed. The Pediatric Epilepsy Side Effect Questionnaire (PESQ) will be completed by participant's parent/ legal guardian to assess for any adverse events and tolerability.

Week 8: Participant to return to The Hospital for Sick Children. Study treatment increased as tolerated by 2mg/kg/day CBD, neurological and physical examination will be performed, weight recorded, seizure diary evaluated. Medical history including concomitant medications will be reviewed. If at maximally tolerated study treatment dose as determined by study team, then bloodwork will be performed (CBC, LFT, and Renal profile and trough AED levels) and QOLCE completed by caregiver/parent. The Pediatric Epilepsy Side Effect Questionnaire (PESQ) will be completed by parent/legal guardian to assess for any adverse events and tolerability.

Week 12: Participant to return to The Hospital for Sick Children for clinical evaluation, which includes an interview to assess current clinical condition, any participant, parent/

legal guardian concerns related to TIL-TC150 and assess for any adverse effects and tolerability by interview. A neurological and physical examination will be performed, weight recorded, seizure diary evaluated. Medical history including concomitant medications will be reviewed. Participant should be on maximal dose of 8mg/kg/day or max tolerated dose now, or on maximally tolerated dose (as determined by study team). If at maximally tolerated study treatment dose as determined by study team, then bloodwork will be performed (CBC, LFT, and Renal profile and trough AED levels). The Pediatric Epilepsy Side Effect Questionnaire (PESQ) will be completed by participant parent / legal guardian to assess for any adverse events and tolerability.

Week 16: Participant to return to The Hospital for Sick Children for clinical evaluation, neurological and physical examination will be performed, weight recorded, and seizure diary will be evaluated. Medical history including concomitant medications will be reviewed. If target dose only reached at this stage blood work to be done now, if previously performed at target or maximally tolerated doses no need to repeat. The Pediatric Epilepsy Side Effect Questionnaire (PESQ) will be completed by participant parent/legal guardian to assess for any adverse events and tolerability and QOLCE completed by caregiver/parent between weeks 16 – 20. In addition, the family will be contacted by clinical psychology to complete a follow-up Vineland adaptive behaviour assessment to measure any changes in behaviour.

Between week 16 and 20 an ambulatory EEG study will be performed at maximal study treatment doses and the completed seizure diary will be collected.

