## Study Summary

|                                       |  |
|---------------------------------------|--|
| Title                                 | Cannabinoid Therapy in Medically Refractory Pediatric Epilepsy – Phase 1: Dosing and Tolerability Study of a Cannabidiol-Rich Whole Plant Extract of Cannabis.   |
| Short Title                           | Cannabinoid Therapy for Pediatric Epilepsy   |
| Phase                                 | 1  |
| Methodology                           | Open-label Intervention  |
| Study Duration                        | 20 weeks to primary analysis with continued follow-up until 64 weeks completed   |
| Study Center                          | The Hospital for Sick Children, Toronto Ontario  |
| Objectives                            | To determine the tolerability and optimal dose of 50:1 ratio CBD:THC Cannabis extract as an adjunct treatment in children with severe drug resistant epilepsy  |
| Number of Subjects                    | 20   |
| Diagnosis and Main Inclusion Criteria | Patients with Dravet Syndrome

Between ages of 1 and 18 years old male or female

Must have failed 2 AEDs at therapeutic doses and be on current regimen of 1-4 AEDs which have been stable doses for 4 weeks  |
| Study Product, Dose, Route, Regimen   | TIL-TC150 Oil is the study product
The active ingredients in TIL-TC150 Oil are THC and CBD, present in a 1:50 ratio. These active ingredients are derived from Cannabis sativa L. strains produced by Tilray and suspended in a grape seed oil. This suspension is administered at a dose of 2mg/kg/day CBD divided BID and titrated up to a maximal dose of 16mg/kg/day CBD (or maximal tolerated). |
| Duration of Administration            | Study period: primary safety and outcome data at 20 weeks with longer follow-up of safety and tolerability in those who chose to continue after the 20-week period and will be followed up to 64 weeks.  |
| Reference Therapy                     | None   |
| Statistical methodology               | The primary aims of this study are to determine the maximal tolerated dose of TIL-TC150 Oil Cannabis Extract in children with drug resistant epilepsies. Descriptive statistics will be used to quantify the frequency and severity of adverse events that are   |

|  |  |
|--|--|
|  | reported for the various dosages that are employed |
|--|--|

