### 3.2 Intervention period (20 weeks)

Following the pre-intervention assessment of baseline seizure frequency, the participant will commence TIL-TC150 product. The initial dose is 2mg/kg/day CBD divided twice daily with weekly titration as described below in section 5. Study treatment will be increased each week as tolerated by 2mg/kg/day CBD. Week 8 should be the last increase if the participant increases by this schedule. The maximal dose is 16/mg/kg/day CBD.

During this time there will be regular communication and clinic visits with the investigator team, as detailed in section 5. Once 16 weeks of therapy have been completed, participants will enter a 4 week interim analysis period, during which time they continue the TIL-TC150 at an unchanged dose and a 4 week seizure diary and a 24 hour ambulatory EEG recording will be performed and compared with the pre-intervention seizure frequency.

This primary outcome data regarding safety, tolerability, dosing and secondary seizure outcomes will be reported at this time point.

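### Section 5.6, Week 12, gives the maximal dose as 8 mg/kg/day CBD, but the protocol's maximum is 16 mg/kg/day (minor)

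*Combined protocol and SAP*

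**What the plan says.** The dosing rule is in Section 5.2: start at 2 mg/kg/day CBD at Week 0 and raise by 2 mg/kg/day every 7 days, as tolerated, up to 16 mg/kg/day. Section 1.5 and the Study Summary give the same start and ceiling. Section 3.2 states "The maximal dose is 16/mg/kg/day CBD". In the Section 5.8 table the dose rises at each of Weeks 1 to 7, reaches 16 at Week 7, and continues at 16 from Week 8, including the Week 12 row. Section 5.7 carries 16, or the child's own maximally tolerated dose, into Week 28.

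Section 5.6 sets out the visits one by one. Its Week 8 text still provides for a step: "Week 8: Participant to return to The Hospital for Sick Children. Study treatment increased as tolerated by 2mg/kg/day CBD".

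The Week 12 visit text in Section 5.6 differs: "Participant should be on maximal dose of 8mg/kg/day or max tolerated dose now". It then makes the bloodwork (blood count, liver and renal tests, trough AED levels) conditional on the child being at the maximally tolerated dose in the study team's judgement.

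The Week 16 text allows for late titration, "If target dose only reached at this stage blood work to be done now", and adds "if previously performed at target or maximally tolerated doses no need to repeat". From Week 16, under Section 3.2, children enter a four-week period in which "they continue the TIL-TC150 at an unchanged dose". Section 3.4 makes the maximal safely tolerated dose in the study population the primary endpoint.

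**The concern.** A dosing and tolerability study should have one maximal dose. Here the visit-by-visit text gives a second one, at half the value, and at a visit where staff decide whether titration is complete and whether the at-dose blood tests are due.

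The child to consider is one whose steps have slipped and who is tolerating 8 mg/kg/day at Week 12. Under Section 5.2 this child should keep going up. The Week 12 sentence could be read as saying the maximum has been reached. Two things could follow:

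- Titration stops at 8, and the doses from 10 to 16 are not tried in that child.
- The at-dose bloodwork and AED levels are drawn at 8, the child then goes higher, and the Week 16 text says there is no need to repeat them. The next scheduled draw in Section 5.7 is one sample somewhere in Weeks 40 to 64, for children who continue. Section 1.7.1 warns that CBD may raise the levels of concomitant AEDs, which is why those levels should be taken at the final dose.

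**Working it through.** **Inputs.** Start 2 mg/kg/day at Week 0; step 2 mg/kg/day every 7 days; ceiling 16 mg/kg/day (Sections 1.5 and 5.2). Weekly doses from the Section 5.8 table. Week 12 figure of 8 mg/kg/day (Section 5.6).

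**Step 1: reproduce the schedule.** On-schedule dose at week w = min(16, 2 + 2w).

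| Week | 0 | 1 | 2 | 3 | 4 | 5 | 6 | 7 | 8 | 12 |
|---|---|---|---|---|---|---|---|---|---|---|
| mg/kg/day | 2 | 4 | 6 | 8 | 10 | 12 | 14 | 16 | 16 | 16 |

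This matches each of these rows in Section 5.8. Steps needed: (16 − 2)/2 = 7, so the ceiling is reached at Week 7 (day 49).

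**Step 2: place the Week 12 figure.** Solving 2 + 2w = 8 gives w = 3, so 8 is the on-schedule dose at Week 3. As a share of the ceiling, 8/16 = 0.50. An on-schedule child at Week 12 has been on 16 for 12 − 7 = 5 weeks, at twice the figure that 5.6 calls maximal. The two statements cannot both be right.

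**Step 3: the child who could be affected.** Take a child who has only just reached 8 at Week 12, which is 12 − 3 = 9 weeks behind schedule. Steps remaining under 5.2: (16 − 8)/2 = 4. Weekly steps give 10, 12, 14 and 16 at Weeks 13, 14, 15 and 16, so 16 is reached at 12 + 4 = Week 16, when the unchanged-dose period begins. A child who reached 8 at Week 11 and steps up at Week 12 reaches 16 at Week 15. Full titration is therefore still possible within the plan, and Section 5.6 at Week 16 provides for it.

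**Step 4: children who are not affected.** A child on schedule passed 8 at Week 3. A child held at 8 because a higher dose was not tolerated is correctly at the maximally tolerated dose. Only a child who is late but still tolerating each step is left.

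**Step 5: how many.** The documents give no rate of delayed titration. Each such child would be 1/20 = 5% of the planned sample. The number could be zero.

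**The case against.** The strongest reply is that the sentence does little work. It describes where a child is expected to be at Week 12 and does not tell anyone to stop. The dosing instruction is Section 5.2, which runs to 16. The Week 12 blood draw is triggered by the study team's judgement that the child is at the maximally tolerated dose, not by the figure 8, and the 5.8 row for the same visit shows 16. The dosing schedule is also re-evaluated at every visit and contact (Section 7.1), and the note under the 5.8 table allows an extra AED level if toxicity is suspected. All of this stands, and it is why the point is minor. It does not make the figure right. The sentence also allows for a tolerated dose, but only as an alternative to a maximum that is wrong by half. Nor can 8 be read as one of two daily doses (16/2 = 8), because the text says per day.

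A reader might also infer three stronger claims that the documents do not support:

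- *That the Week 8 step in 5.6 allows 18 mg/kg/day.* The uncapped sum is 2 + 2 × 8 = 18, but the step is subject to tolerability and to the 16 ceiling in 3.2 and 5.2. It suits a child who is behind schedule.
- *That Section 3.2 sets a different titration.* It says "Week 8 should be the last increase if the participant increases by this schedule", whereas 5.8 shows the last step at Week 7. This is loose wording, the next sentence gives the 16 ceiling, and no dose changes.
- *That the primary endpoint would be biased.* Section 3.4 states the endpoint for the study population and defines no value per child. Section 8.1 plans descriptive statistics only.

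**Conclusion.** The Week 12 maximum in Section 5.6 contradicts the rest of the protocol: 8 against 16 mg/kg/day CBD, or 50% of the intended ceiling. No reading of the sentence as written reconciles the two.

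The consequence is small and conditional. It needs a child with markedly delayed titration who is tolerating 8 at Week 12, and a team that relies on this one sentence without consulting 5.2 or 5.8. If both hold, up to four dose steps could be forgone, or the at-dose bloodwork and AED levels could be taken at 8 and not repeated at the final dose. How often this would happen cannot be estimated from the documents. No sample size, power or error-rate figure depends on it. The point is minor. The error itself is certain; harm from it is only possible.

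**What to change.** In Section 5.6, Week 12, change 8 to 16, so that the sentence says the child should by now be receiving 16 mg/kg/day CBD or the maximally tolerated dose, as judged by the study team. The same edit can drop the repeated mention of the tolerated dose in that sentence. Sections 5.2, 5.7 and 5.8 need no change.

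The cost is one wording edit, with no added visit, test or participant. If the text is open anyway, the Week 8 wording in 3.2 and 5.6 could be aligned with the 5.8 table, but that is optional tidying and does not affect any dose.
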